4.3 Prior and concomitant therapies

4.3.1 Definition

Previous therapies (drugs and/or procedures) are defined as therapies that have been stopped within 12 weeks prior to the investigational product application.

Concomitant therapies are defined as follows:

- any existing therapies ongoing at the time of the baseline visit , or
- any changes to existing therapies (such as changes in dose or formulation) during the course of the clinical trial, or
- any new therapies received by the subject since the baseline visit

4.3.2 Categories

The following two categories will be considered for previous and concomitant therapies:

- Drugs/therapies including, but not limited to, prescription, over-the-counter (OTC), birth control pills/patches/hormonal devices, vitamins, moisturizers, sunscreens, herbal medicines/supplements, and homeopathic preparations.
- Medical and surgical procedures including, but not limited to, laser/radiation procedures, dermal fillers, X-rays, etc.

4.3.3 Recording

Previous and concomitant therapies will be recorded on the Drugs/Therapies Form (for drugs/therapies) and/or on the Medical and Surgical Procedures form (for medical/surgical procedures) in the case report form (CRF).

Concomitant therapies will be recorded, reviewed, and updated at each trial visit.

Every attempt should be made to keep concomitant therapy dosing and regimen constant during the study. Any change to the concomitant therapy should be noted on the CRF. Any new concomitant therapy or modification of an existing therapy may be linked to an adverse event (AE). A corresponding Adverse Event Form must be completed to account for the change in therapy, except in some cases such as therapy used for prophylaxis, dose modification for a chronic condition, etc.

4.3.4 Authorised therapies during the clinical trial.

Unless listed in the exclusion criteria above or in the prohibited therapies (see sections [4.2.2](#) and [4.3.5](#)), all therapies are authorised.

Subject may use the sunscreen and moisturizer provided for the trial as required for the symptomatic relief of skin dryness or irritation (use of moisturizer other than the provided one will be captured in the CRF as concomitant therapy).

Note: It is preferred that a moisturizer (provided one or a one not containing alpha hydroxy acid) be added to the treatment regimen as opposed to implementing an altered dosage regimen.

4.3.5 Prohibited therapies during the clinical trial

The following therapies are prohibited because they may interfere with the efficacy and/or safety assessment of the investigational product, or because they may interact with the metabolism of the investigational product:

- On the anatomical area, all topical treatment, medical/surgical procedures listed as exclusion criteria (section [4.2.2](#)).
- All systemic therapies listed in exclusion criteria (section [4.2.2](#)).
- Any other drugs/procedures which in the investigator's judgment are liable to interfere or interact with the efficacy or safety of Luxerm®.
- Any UV-therapy should be discontinued before treatment.

- As a general precaution, sun exposure of the treated anatomical area should be avoided for about 2 days following treatment
- If any outdoor sun exposure the subject will be recommended to apply the provided sunscreen.
- Any treatment including cryotherapy is prohibited except at the end of the study to treat AK lesions at last visit after study clinical assessments.
- If subject presents mild/moderate/severe AKs outside anatomical area and investigator wishes not to wait the end of study before treating them, he/she can do so but in this case only cryotherapy can be used. In order to avoid interference with subject pain assessment, it should be done once all study assessments, including subject questionnaire completion, have been performed at the baseline visit.

If prohibited therapies become a necessary treatment for the safety or best interest of the subject, *GALDERMA R&D* will be notified to discuss possible alternatives prior to administration of a prohibited therapy and to discuss the pertinence and the modalities for the subject to continue in the clinical trial.

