4.4 Procedures / reasons for discontinuation

An Investigator may decide to discontinue a subject from the clinical trial for safety reasons.

Although the importance of completing the entire clinical trial should be explained to the subject by the clinical trial personnel, any subject is free to discontinue his/her participation in this clinical trial at any time and for whatever reason, specified or unspecified, and without prejudice.

Subjects who discontinue the clinical trial prematurely should be fully evaluated, whenever possible. The procedures designated for the week 12 post-treatment visit will be performed for all premature discontinuation subjects. The appropriate CRF pages should be completed.

For all subjects who prematurely discontinue the clinical trial, the reason must be carefully documented by the investigator on the Exit Form, and, if applicable, on the Adverse Event Form if discontinuation is due to an AE.

At 1 week post-baseline the investigator will call the subject if he has not heard from the subject since baseline visit, to check if the study treatment has been performed:

- **If the subject was not able to perform the study treatment during the week post-baseline due to bad weather conditions, another additional period of maximum 7 days is offered to perform the study treatment.**
- **For an additional period greater than 7 days the decision to maintain the subject in the study will be based on discussion between investigator and sponsor.**

- If the subject decides to stop his participation for whatever reason, he/she will be asked to return the study product to the site. The study product must not be reallocated to another subject and should be discarded from the study product stock. Investigator has the possibility to replace the subject.**

In the case of early termination, the investigator should ensure that the subject receives appropriate therapy for his/her condition.

GALDERMA R&D may also decide to prematurely terminate or suspend the clinical trial or the participation of a subject in the clinical trial.

All data gathered on the subject prior to termination will be made available to *GALDERMA R&D*.

Reasons for clinical trial completion/discontinuation, as listed on the Exit Form of the CRF are described below:

Normal study Completion	Subject completes the clinical trial as planned in protocol.
Pregnancy	Withdraw the subject from the clinical trial following the procedure described in the protocol section 8.3

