5.4 Clinical trial flow chart

STUDY PROCEDURES	Baseline Visit 1 D0	Treatment Day ^g (at patient's home)	Day 1 post- treatment Visit 2 (± 2 days)	Week 12 post- treatment Visit 3 (± 7 day)
Informed consent	X			
Inclusion/Exclusion criteria	X			
Demography/Medical history	X			
Previous therapies ^a	X			
Urine pregnancy test ^d	X			X ^e
Concomitant therapies	X		X	X ^e
Lesion mapping and counting ^c	X			X ^e
Sunscreen application		X		
Skin preparation	X ^k	X ⁱ		
Luxerm® application and DL treatment session		X		
Lesion response using the transparent plastic sheet (for initial treated AK lesions)				X ^e
Clinical assessment of skin aspect for AK lesions in complete response				X ^e
Count of new AK lesions using the transparent plastic sheet				X
Photodamage Dovers assessment	X			X ^e
Adverse events ^b (including local skin reaction)	X		X	X ^e
Subject questionnaire		X ^f		X ^e
Physician questionnaire ^j				X ^e
Photographs ^h	X			X ^e
Treatment Dispensed	X			
Subject Compliance			X	
Study treatment return			X	
Exit form				X ^e

- a. Treatment that continues after visit 1 should be recorded on the concomitant therapies form of the CRF.
- b. Adverse Events have to be collected from the moment the Informed Consent signature is obtained and recorded on the AE form of the CRF.
- c. Actinic keratosis lesions in the treated area will be counted. For accurate counting, lesion localization and follow-up, a clear plastic sheet will be placed over the anatomical area of the face or scalp being treated and other anatomical landmarks will also be marked on this sheet
- d. For subject of childbearing potential: The determination of UPT is mandatory at baseline and at week 12 or before if there is early termination. UPT must have a sensitivity of less than at least 25IU/L. In case of positive UPT during the study the investigator will withdraw the subject from the clinical trial according to the procedure for reporting pregnancy details in the protocol.
- e. To be performed at week 12 or before in case of early termination.

- f. After the 2 hours daylight exposure.

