- c) Affix the tear-off portion of the label on the product dispensation log and report the required information on the labels if applicable.
- d) Provide appropriate verbal and written instructions on how to properly use the investigational product(s) and how to perform the treatment procedure (see instruction in section 6.1.4)
- e) Emphasize the importance of complying with the given instructions and treatment; instruct the subject to bring back the dispensed investigational product(s) at the next visit.

12. Dispense to the subject any associated non-investigational product(s).

13. Give and provide instruction to the subject how to use the provided Moisturizer in case some tolerability reactions occur (see 0).

14. Remind the Subject to avoid sun exposure of the treated anatomical area and the use of sunscreen for about 2 days following treatment procedures.

15. Assess the skin photodamage of the selected anatomical area using the Dover's modified global photodamage score (see 7.4.1).

16. Provide guidance on the satisfaction questionnaire (see appendix 1) and ask the subject to fill it out the day of treatment after the daylight exposure. Remind the subject to return it at the next study visit (Day 1 post-treatment).

17. *For selected sites only*, take photographs of the target anatomical area according to the provided procedure only if subject has agreed on the approved photo release consent form.

18. For all female subjects of childbearing potential, emphasize the guidelines about contraception and risks in case of pregnancy.

19. Instruct the subject to call you the day of treatment to confirm the treatment has been well completed and to schedule the next study visit (Day 1 post-treatment). **If you have not heard of subject one week after the baseline, contact him/her to get news and refer to section 4.4.**

At a minimum, tasks numbered 9, 10 and 15 have to be performed by a Dermatologist.

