5.5.2 Visit 2 (day 1 after treatment ±2 days)

1. Question the Subject about AEs by asking an open-ended question taking care not to influence the Subject's answer, such as "Have you noticed any change in your health since the last visit, including any potential skin reaction in the treated anatomical area?". Record all events (including Local Skin Reaction), as appropriate on the corresponding CRF pages.
2. Enquire whether any concomitant therapies have been added, stopped, or changed since the subject's last visit. Document all changes in the CRF.
3. Collect the first subject questionnaire and ensure it is fully completed including the SIN and the treatment date. Report the subject's questionnaire in the eCRF.
4. Assess subject's compliance with regard to the study treatment. Based on the subject's questionnaire and discussion with the subject. Check the study treatment has been performed according to the provided instructions. Report the results in the eCRF.
5. Ensure that the subject has returned all used/unused investigational product.
 - a) Missing investigational product must be documented in the product dispensation log comments section and on other accountability form.
 - b) For all female subjects, reiterate the guidelines about contraception and risks in case of pregnancy.
6. Schedule the next follow up visit, week 12 (±7 days).

In case of early termination of the Clinical Trial for whatever reason:

- a) The subject will be fully evaluated.
- b) The procedures designated for the week 12 visit should be performed.

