7.3.2 Subject's self-assessment of pain

After the treatment procedure when 2 hours daylight exposure is completed, the subject will be requested to assess the maximal pain felt during the duration of the light exposure. The pain sensation will be assessed on an 11-point Numeric Rating Scale (NRS), where 0 = no pain at all and 10 = extreme pain and will be reported by the subject in the first subject questionnaire.

Table 5 - NRS - subject's self-assessment of pain

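### Section 4.3.5 times off-area cryotherapy by a questionnaire completed at baseline, but the only questionnaire with a pain rating is completed on the treatment day

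*Combined protocol and SAP*

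**What the plan says.** Section 4.3.5 starts from a general rule: "Any treatment including cryotherapy is prohibited except at the end of the study". An exception follows for lesions outside the treated anatomical area. An investigator who does not want to leave them until the study ends may treat them, by cryotherapy only. The exception carries one timing condition, with its purpose stated. It reads: "avoid interference with subject pain assessment, it should be done once all study assessments, including subject questionnaire completion, have been performed at the baseline visit".

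The rest of the protocol places the questionnaire and the pain rating as follows.

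- Section 5.5.1, item 16 (baseline): the investigator explains the questionnaire and is to "ask the subject to fill it out the day of treatment after the daylight exposure".
- Section 5.4, flow chart: the subject questionnaire is marked under the treatment day and week 12, with nothing under baseline. Footnote f times the first one: "After the 2 hours daylight exposure".
- Section 7.3.2: once the exposure is over, "the subject will be requested to assess the maximal pain felt during the duration of the light exposure". The answer goes into the first questionnaire.
- Section 5.5.2, item 3 (visit 2): "Collect the first subject questionnaire and ensure it is fully completed including the SIN and the treatment date".
- Section 4.4: if bad weather prevents treatment in the first week, "another additional period of maximum 7 days is offered to perform the study treatment". Beyond that, the investigator and the sponsor settle the matter together: "For an additional period greater than 7 days the decision to maintain the subject in the study will be based on discussion".

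**The concern.** The condition in 4.3.5 joins an event (questionnaire completed) to a visit (baseline) at which that event does not happen. Two sites could act on the sentence in opposite ways and each claim to have followed it.

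What is at stake is the maximal-pain rating, one of the two safety variables in section 9.1.1.2. Better tolerability in terms of pain is also part of the clinical hypothesis in section 3.2. Appendix 1, item 16 limits the rating to the period of exposure but not to the treated skin. Appendix 1, item 6 lists scalp, forehead, right cheek, left cheek and chin as separate areas, so a lesion outside the study area may be on neighbouring skin. The sponsor evidently thought interference possible, since the sentence was written to prevent it.

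**Working it through.** The plan gives no figure on this point, so there is none to reproduce. The check compares the condition with the schedule and then works out the interval in days.

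**Schedule of subject questionnaires and pain ratings (sections 5.4, 7.1 and 7.3.2; Appendices 1 and 2)**

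| Time point | Questionnaires completed | Pain ratings |
|---|---|---|
| Baseline | 0 (guidance only) | 0 |
| Treatment day, after exposure | 1 (Appendix 1) | 1 |
| Visit 2 | 0 (Appendix 1 collected) | 0 |
| Week 12 or early termination | 1 (Appendix 2) | 0 |

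**Interval from baseline to the pain rating**

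- Inputs: treatment within 1 week (± 7 days) of baseline (section 5.1), and the further 7 days in section 4.4.
- Earliest: 7 − 7 = 0 days.
- Latest without discussion with the sponsor: 7 + 7 = 14 days.
- With discussion: longer, with no upper limit given.

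**Latest visit 2 for a subject treated on day 14**

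- Input: visit 2 on day 1 after treatment, ± 2 days (section 5.5.2).
- 14 + 1 + 2 = day 17 after baseline.

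**The two readings of the condition**

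1. *The named visit governs.* Cryotherapy is allowed on day 0 once the baseline assessments are done. The pain rating follows on the same day at the earliest and up to 14 days later without an extension. The rule then permits what it was written to prevent.
2. *The questionnaire condition governs.* It cannot be satisfied at baseline. The exception stays closed until after the treatment day, and the reference to baseline is an error.

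**Do other provisions settle it?** The general ban is what the exception overrides, so by itself it does not say when the exception opens. The item in the same list about drugs or procedures that the investigator judges likely to interfere gives no timing. Guidance on the questionnaire at baseline is not completion of it. The other two safeguards for the pain rating are anchored correctly: section 5.6, item 1 (pain relief) and section 6.2 (moisturizer) both run until the self-assessment is complete. Only the cryotherapy rule is tied to baseline.

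**The case against.** The best defence is that the sentence, taken literally, fails safely. The permission depends on questionnaire completion. If that cannot happen at baseline, the exception does not open there and the general ban continues. The sentence also states its purpose, and only one questionnaire holds a pain rating, so a careful reader would wait for that one. This carries weight: the pain rating is exposed only if a site follows the visit label and overlooks the questionnaire condition. It does not remove the conflict, because the visit label is explicit and a busy site may well act on it.

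The route to harm is also thin. The cryotherapy is optional, lies outside the treated area and will often be separated in time from the exposure. The rating asks about pain during the exposure, not since baseline. Section 9.1.4 plans no inferential statistics, and the main objective is satisfaction. All of this stands and keeps the point minor.

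A reader might infer that the pain results will be biased, or that the protocol plainly authorises cryotherapy before the rating. The documents support neither. They give no frequency of off-area cryotherapy and no effect of it on the rating, and the questionnaire condition points away from early cryotherapy.

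**Conclusion.** The timing sentence in section 4.3.5 is wrong as written, and nothing else in the protocol corrects it. It is an inconsistency of wording in an operative rule; the intended design, protecting the pain rating, is clear and not in dispute.

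The point is minor. Any effect is confined to the descriptive summary of maximal pain, which has no threshold or test attached. Its size cannot be derived and none is claimed. Procedures are recorded under section 4.3.3, so affected subjects could be identified afterwards.

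The conclusion rests only on comparing section 4.3.5 with the visit schedule. The range of 0 to 14 days assumes no extension agreed with the sponsor.

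**What to change.** In section 4.3.5, keep the stated purpose and replace the timing condition with: *only after the treatment-day questionnaire (Appendix 1) has been completed and collected, i.e. at visit 2 after that visit's assessments, or later.* This uses the same anchor as the pain-relief and moisturizer rules.

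The change is one sentence. It has two downsides.

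- **Delay.** Optional off-area cryotherapy moves from day 0 to at most about day 17, or later if the treatment window is extended. Day 0 is the fair starting point, because the exception exists for investigators who do not want to wait until the study ends.
- **Overlap of skin reactions.** Cryotherapy at visit 2 falls within days of the study treatment, when local skin reactions are being collected as adverse events. Appendix 2, items 2 and 4 later ask how much skin reactions bothered the subject and how long they caused embarrassment. Cryotherapy at baseline could affect these answers too, so the problem is not wholly new. Recording the date and site of each cryotherapy on the existing Medical and Surgical Procedures form would help to tell the two sources apart.

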4.4 Procedures / reasons for discontinuation

An Investigator may decide to discontinue a subject from the clinical trial for safety reasons.

Although the importance of completing the entire clinical trial should be explained to the subject by the clinical trial personnel, any subject is free to discontinue his/her participation in this clinical trial at any time and for whatever reason, specified or unspecified, and without prejudice.

Subjects who discontinue the clinical trial prematurely should be fully evaluated, whenever possible. The procedures designated for the week 12 post-treatment visit will be performed for all premature discontinuation subjects. The appropriate CRF pages should be completed.

For all subjects who prematurely discontinue the clinical trial, the reason must be carefully documented by the investigator on the Exit Form, and, if applicable, on the Adverse Event Form if discontinuation is due to an AE.

At 1 week post-baseline the investigator will call the subject if he has not heard from the subject since baseline visit, to check if the study treatment has been performed:

- **If the subject was not able to perform the study treatment during the week post-baseline due to bad weather conditions, another additional period of maximum 7 days is offered to perform the study treatment.**
- **For an additional period greater than 7 days the decision to maintain the subject in the study will be based on discussion between investigator and sponsor.**

- If the subject decides to stop his participation for whatever reason, he/she will be asked to return the study product to the site. The study product must not be reallocated to another subject and should be discarded from the study product stock. Investigator has the possibility to replace the subject.**

In the case of early termination, the investigator should ensure that the subject receives appropriate therapy for his/her condition.

GALDERMA R&D may also decide to prematurely terminate or suspend the clinical trial or the participation of a subject in the clinical trial.

All data gathered on the subject prior to termination will be made available to *GALDERMA R&D*.

Reasons for clinical trial completion/discontinuation, as listed on the Exit Form of the CRF are described below:

Normal study Completion	Subject completes the clinical trial as planned in protocol.
Pregnancy	Withdraw the subject from the clinical trial following the procedure described in the protocol section 8.3
Adverse Event	Complete CRF Adverse Event Form.
Withdrawal by subject	Includes consent withdrawal, subject relocation, schedule conflicts, etc... Does not include AE. Explain the reason for withdrawal in the comments section of the CRF Exit Form.
Protocol Violation	Explain the violation in the comments section of the CRF Exit Form
Lost to Follow-up	Confirm with 2 documented phone calls and a certified letter (delivery receipt requested) without response. Explain in the comments section of the CRF Exit Form.
Other	This category is to be used for a subject who discontinues for a reason other than those specified in the predefined categories above. Explain the reason for discontinuation in the comments section of CRF Exit Form.

If reason for discontinuation is “withdrawal by subject” or “other”, the subject must be questioned to rule out the possibility of an AE; this should be documented in the CRF.

